#### *User KAB Survey*

Individuals meeting any of the following criteria will be excluded from the study:

- Participation in a clinical study that may interfere with participation in this study (i.e., clinical studies assessing the efficacy of long acting injectables for PrEP), during the study period.

### *Apretude Supports Program Database Analysis*

Individuals within the Apretude Supports Program database meeting any of the following criteria will be excluded from the study:

- Initiated CAB-LA outside of the Apretude Supports Program (i.e., with a lack of historical data on CAB-LA injection dates prior to entry in the PSP).

## **7.3. Variables**

### **7.3.1. Exposure Definitions**

#### *HCP Survey*

For HCPs, exposure will be defined as having prescribed or managed use of CAB-LA for the prevention of HIV-1 among individuals at high risk in Canada eligible for CAB-LA based on the HC indication.

*User Survey*

For CAB-LA users, exposure will be defined as having previously initiated CAB-LA for the prevention of HIV-1. In the survey, this is defined as having received at least one dose of CAB-LA at the time of survey enrolment.

*Apretude Supports Program Database Analysis*

For CAB-LA users, exposure will be defined as having initiated CAB-LA for the prevention of HIV-1. In the Apretude Supports Program database analysis, this is defined as enrollment and initiation of CAB-LA through the Apretude Supports Program within the ascertainment period (i.e., have received at least one injection of CAB-LA, with the first dose taking place between July 2024 and October 2026). Data will be included for users until the end of the follow-up period (October 2027) or until discontinuation.

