#### Secondary Objectives

For the secondary objectives 1 through 8, primary data will be collected through surveys administered to HCPs and CAB-LA users (see Table 1). The HCP and user surveys will be conducted at one time point corresponding to approximately 18-months +/- 2-month post CAB-LA launch (December 2025 to April 2026).

For secondary objectives 6 and 9 a retrospective cohort analysis will be executed using data from the CAB-LA patient support program (“Apretude Supports Program”) database (Table 1), which captures basic CAB-LA use information for all individuals enrolled in the program. In the Apretude Supports Program database, data will be included for individuals initiating CAB-LA between 15 July 2024 (the date of commercial availability in Canada) and October 2026 (the ascertainment period). Within this ascertainment period, eligible individuals will be indexed into the cohort at the date of initiation of CAB-LA injections. An ascertainment period end date of October 2026 was chosen to allow for a minimum 1-year follow-up from initiation of CAB-LA (index date) given final analysis will take place November 2027. An interim analysis is planned for Q1/Q2 2026 for data available up to that time point (July 2024 to Q1/Q2 2026).

Two separate sources of CAB-LA user demographic data will be available in this study to address secondary objective 6: one from the CAB-LA user survey and one from the Apretude Supports Program database. If linkage between the survey data and PSP database is feasible, the analysis will aim to combine the data to gain further insights particularly in regards to user factors impacting utilization patterns. The CAB-LA user survey data will be used to explore relationships between demographic characteristics and objectives 7 and 8, while the Apretude Supports Program data will inform analyses related to objective 9.

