**Table 12. Outcome assessed for secondary objective #9**

Category	Sub-category	Details
Utilization patterns	• Use of oral lead-in	
 
▪ Frequency of use
 
▪ Duration of use
 

	• Use of oral bridging	
	• Adherence to CAB-LA	
 
▪ Measured as proportion of days covered (PDC)                             
 
○ Ratio of number of days the user is covered by the medication during a specific period to the total number of days within that period                                     
 
• Measured on user’s coverage (days supplied) with CAB-LA
 
 
 
 
 

Category	Sub-category	Details
		
 
Based on available follow-up time within the Apretude Supports Program database
 

	
 
Timing of injections (relative to labeled dosing schedule)
 
	
 
Early, on-time, late (with 7-day grace period)
 

	
 
Gaps in therapy
 
	
 
Missed injections (relative to labeled dosing schedule), reasons for missed injections
 
Missed injections being planned or unplanned
 
Use of oral bridging, planned or unplanned                             
 
Type and frequency of oral bridging agents used
 
Duration of oral bridging
 
 
 

	
 
Persistence on CAB-LA
 
	
 
Time to discontinuation
 
% of users who remain on drug, and are still at risk of HIV infection, at end of follow-up (will depend on data availability for at-risk status, either through PSP variables or through linkage with survey data)
 

	
 
Discontinuation
 
	
 
Rates of discontinuation
 
Reasons for discontinuation
 

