## ANNEX 1 TABLES

Variable	Description
Patient ID	Anonymized unique program identification number
Enrolment Date	The date on which the patient was successfully enrolled in the PSP
Patient Status	Current status of patient (On drug, Suspended, Discharged)
Patient Status Date	The date the patient was moved into current status
Appointment Number	Sequential appointment number associated with the appointment
Initiation injection Dosing Schedule	Identifies whether the patient is receiving dosing schedule.
2 nd initiation injection Dosing Schedule	Identifies whether the patient is receiving dosing schedule.
Patient File Appointments	The date on which drug was dispensed and/or administered
Days Supplied	Days of supply for each dispense/administration
Oral Lead-in	Indicator if the patient initiated the optional a lead-in (i.e., flag and/or date)
Injection type	Description of the type of injection (initiation, subsequent, or re-initiation)
First Dose Date	The date on which the patient initiated their 1st dose of APRETUDE injection
Initial Injection Dose	Dosage as indicated in the initial physician order
Current Injection Dose	Dosage as indicated in the most recent physician order
Baseline Target Treatment Date	Most recently set target date. Modification could be due to planned/unplanned missed infusions
Current Target Treatment Date	Target treatment date for that appointment record
Confirmed Appointment Date	The date of appointment
Missed Appointment date	Date of missed appointment(s)
Cancelled/Rescheduled Appointment Date	Date of cancelled/rescheduled appointment(s)
Reason for Missed Injection	Reason provided for cancellation/rescheduling of appointment(s)
Planned/Unplanned Oral bridging	Was the cancellation planned or unplanned
Oral Bridging Agent	The type of oral bridging agent taken from the planned missed injection
Oral Bridging Dose	The dosage of oral bridging agent taken from the planned missed injection
Oral Bridging or Planned Leave Start Date	The date on which the patient initiated cabotegravir tablets or other oral PrEP due to a planned missed injection
Oral Bridging or Planned Leave End Date	The date on which the patient discontinued cabotegravir tablets or other oral PrEP due to planned missed injection
Returned Appointment Date or Target Treatment Date	The target date of administration of APRETUDE following a planned missed injection
Re-initiation appointment date	The date of next scheduled appointment after the missed injection/appointment

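### PSP data end at discontinuation, so PDC covers only time up to the recorded stop and restarts after a recorded discontinuation are lost

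*Protocol*

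**What the plan says.** Section 7.3.1 (Exposure Definitions, Apretude Supports Program Database Analysis) fixes the end of each user's data: "Data will be included for users until the end of the follow-up period (October 2027) or until discontinuation".

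Table 12 in section 7.3.2 lists the outcomes for secondary objective 9. Adherence is PDC, defined as "Ratio of number of days the user is covered by the medication during a specific period to the total number of days within that period". The numerator is "Measured on user’s coverage (days supplied) with CAB-LA". The period is described only as "Based on available follow-up time within the Apretude Supports Program database". Gaps in therapy, persistence (including "Time to discontinuation" and the share still on drug and at risk when follow-up ends) and discontinuation are separate rows.

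Section 7.1, under Secondary Objectives, closes ascertainment in October 2026 "to allow for a minimum 1-year follow-up from initiation of CAB-LA (index date").

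Annex 1 lists the fields in the extract. Injection type is a "Description of the type of injection (initiation, subsequent, or re-initiation"). Patient status can be on drug, suspended or discharged. The re-initiation appointment date is tied to a missed injection or appointment. The only discontinuation date is the day the user was identified as discontinued or as having opted out of the program.

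**The concern.** One rule for ending data is applied to outcomes that need different rules. For time to first discontinuation, follow-up properly ends at the event. For PDC, ending it there removes the uncovered days that follow, so the sooner a user stops, the fewer uncovered days can enter the denominator. For status at the end of follow-up, and for gaps, it removes whatever happens after the recorded discontinuation, including a restart that the injection-type field could identify.

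Section 7.1 secures at least one potential year per user, yet the section 7.3.1 rule takes the rest of that year away from anyone who stops within it. The protocol's rationale (section 5.2) says utilization patterns may inform decisions on population coverage. It also notes that some seroconversions came more than six months after the last dose, and that resistance could develop after stopping. An adherence figure confined to time before the recorded stop does not describe coverage among everyone who initiated.

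**Working it through.** **Step 1. The plan's own figure.** Last index is October 2026 and follow-up ends October 2027. From 31 October 2026 to 31 October 2027 is 365 days, so the stated one-year minimum reproduces. Because only months are given, the range is 335 days (31 October 2026 to 1 October 2027) to 395 days (1 October 2026 to 31 October 2027). This is potential follow-up, before the cut at discontinuation.

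**Step 2. PDC for one user.** The protocol gives no days-supplied values, stopping rates or recording lags, so the following are assumptions. Section 5.1 describes two initiation injections a month apart and then one every two months. I take 30 days of supply for the first injection and 60 for each later one, all on time. Supply after k injections is s = 30 + 60(k − 1). L is the number of days from end of supply to the recorded discontinuation.

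- Period cut at discontinuation: PDC = s / (s + L)
- Fixed period from index: PDC = s / 365

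| Injections | s (days) | Cut, L = 0 | Cut, L = 30 | Cut, L = 60 | Cut, L = 90 | First 365 days |
|---|---|---|---|---|---|---|
| 1 | 30 | 100% | 50.0% | 33.3% | 25.0% | 8.2% |
| 2 | 90 | 100% | 75.0% | 60.0% | 50.0% | 24.7% |
| 3 | 150 | 100% | 83.3% | 71.4% | 62.5% | 41.1% |
| 4 | 210 | 100% | 87.5% | 77.8% | 70.0% | 57.5% |

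In every row the cut PDC exceeds the fixed-window PDC. With two injections it is two to four times as large (50/24.7 to 100/24.7).

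**Step 3. A restart after recorded discontinuation.** Take two injections, discontinued status at day 90, restart at day 210, then full coverage to day 365. Cut PDC is 90/90 = 100%. Over 365 days with the restart counted, it is (90 + 155)/365 = 245/365 = 67.1%. The 120-day gap (210 − 90) does not appear in the data, and if the user is still on drug in October 2027 the status outcome records the opposite.

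**Step 4. Cohort mean.** Let a share d stop after two injections while the rest are fully covered.

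- Fixed 365 days: (1 − d) + d × 90/365. This is 92.5% for d = 10% and 62.3% for d = 50%.
- Cut, no lag: 100% in both cases.
- Cut, L = 30 to 90: (1 − d) + d × 0.75 down to (1 − d) + d × 0.50. This is 97.5% to 95.0% for d = 10% and 87.5% to 75.0% for d = 50%.

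The overstatement relative to the common window is therefore 2.5 to 7.5 points at d = 10% and 12.7 to 37.7 points at d = 50%, depending on the lag.

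**The case against.** Four points can be made in the plan's defence.

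- **Separate constructs.** Table 12 reports adherence, persistence and discontinuation separately. Measuring adherence while on drug, beside persistence, is a coherent scheme. This stands, and it is why the on-treatment PDC should be kept. A reader might infer that early stopping is hidden; it is not, because time to discontinuation and the rates and reasons are all reported.
- **Restarts after missed injections.** A reader might infer that every restart in the database is dropped. The documents do not support that. Annex 1 ties the re-initiation appointment to a missed injection and has a suspended status distinct from discharged. Users who miss an injection or are suspended, and return without a discontinued status, stay in the data with their gaps. Only restarts after a recorded discontinuation are lost. The protocol gives no number for these and does not show that the program keeps recording such users.
- **Full adherence is conditional.** A reader might infer that early stoppers always score 100%. That needs on-time injections and a discontinuation dated at the end of supply. Annex 1 dates it when the user was identified as discontinued, which may be later, and the figure then falls as in Step 2.
- **The window may be set in the SAP.** Table 12 leaves the period open, and the on-drug denominator comes from reading it with section 7.3.1. A PDC window is ordinary SAP content. But the SAP could not count person-time that section 7.3.1 excludes without contradicting it, so the inclusion rule itself has to change.

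The user survey also asks about missed injections, current use and discontinuation (Table 10), which softens the loss. The objective is descriptive, secondary and not mandated by Health Canada.

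**Conclusion.** The point holds in limited form. The rule in section 7.3.1, combined with available follow-up time in Table 12, makes PDC a ratio up to recorded discontinuation over windows of differing length, and it is inflated for early stoppers compared with a common window. For a user who stops after two on-time injections it gives 50% to 100% against about 25%, assuming 30 and 60 days of supply and a recording lag of 0 to 90 days. The cohort effect depends on the share who stop, which the protocol does not state.

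Separately, a restart after a recorded discontinuation and the gap before it are excluded, so that user is misclassified in the end-of-follow-up status outcome. How often this occurs cannot be judged from the protocol. The primary objectives are untouched. This is an inexpensive improvement to a secondary analysis, and whether the fixed-window or the on-treatment PDC is the main measure remains the sponsor's choice.

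**What to change.** **Section 7.3.1.** Include PSP data until October 2027 or exit from the program, regardless of drug discontinuation. Keep discontinuation as the terminating event only for time to first discontinuation. State the closing day in October 2027, since month-level dates leave 335 to 395 days for the last users indexed.

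**Table 12, adherence.** Report PDC over the first 365 days from index beside on-treatment PDC. In the fixed-window row, count days after stopping drug as uncovered and supply from re-initiation injections as covered.

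**Leaving the program versus stopping drug.** The Annex 1 discontinuation date merges the two. Use the Status Reason Discontinued field to separate them. Censor users who left the program or whose reason is unclear, and add a sensitivity row for the unclear cases. Without this step, users who left the program but stayed on drug would be scored as uncovered.

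**Restarts.** Report the number and percentage who re-initiate after a recorded discontinuation and the length of the gap, as far as the database holds records after that date.

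**Cost.** Amended wording, a few extra table rows and a less favourable adherence figure. The fields needed are already in Annex 1. The result depends on how the reason field is coded, which the protocol does not show. At the interim analysis, users indexed less than 365 days before the data cut will not have a complete window and must be shown as such.

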**7.3.2. Outcome Definitions**

The following characteristics and outcomes will be assessed to meet both the primary and secondary objectives for the study. For the HCP and user surveys, the following data will be collected at the time of survey completion, as well as any prior historic data. The time point for survey data collection will be from December 2025 to April 2026 for the primary and secondary objectives.

The HCP and user surveys are included in Annex 2, and the variables included in the Apretude Supports Program are included in Annex 1.

***Demographic and clinical characteristic variables:***

**Table 2. Demographic and clinical characteristics included in the HCP survey**

HCP Survey
• Age
• Gender identity
• Sex
• Province or territory of practice
• Type of HCP (e.g., physician, nurse, pharmacist) and HCP specialty (e.g., general practitioner, infectious disease specialist)
• Prescriber status
• Prior training in infectious disease and/or HIV medicine
• Practice setting/type (e.g., hospital, outpatient clinic, pharmacy, family health clinic)
• Years of practice in current role

 
• Years/months of experience with oral PrEP
 

 
• Experience working with CAB LA
 

 
• Number of CAB-LA users seen in practice per year
 

 
• Receipt of information on the use of CAB-LA through a ViiV representative
 

**Table 3. Demographic and clinical characteristics included in the user survey**

User Survey

 
• Age
 

 
• Sex (assigned at birth)
 

 
• Gender identity
 

 
• Sexual orientation
 

 
• Race
 

 
• Province or territory of residence
 

 
• Population density (urban vs. rural)
 

 
• Marital status
 

 
• Educational attainment
 

 
• Employment status
 

 
• Household income level
 

 
• Drug/substance use, alcohol use, smoking status
 

 
• Types of sexual activity
 

 
• Number of sexual partners
 

 
• Risks in the past 6 months that are related to:                             
 
○ Engagement in sex work
 
○ Getting diagnosed with a sexually transmitted infection
 
○ Injection of non-prescribed drugs e.g., heroin, fentanyl, methamphetamine
 
○ Use of non-injectable sex-enhancing drugs not prescribed by an HCP
 
○ Having a sex partner with HIV with an unknown or undetectable viral load
 
 
 

**Table 4. Demographic and clinical characteristics included in the Apretude Supports Program database analysis (as data availability permits)**

Apretude Supports Program database analysis

 
• Use of oral lead-in
 

 
• Number of injections received to-date
 

 
• Number of oral bridges, type of oral bridging used
 

***Outcome Variables – Primary Objective***

The HCP and user surveys will collect data on HCP and user access to the relevant aRMMs, as well as their knowledge and behaviours related to the key risk messages within the aRMMs. Additionally, the HCP survey will collect data on HCP attitudes related to the key risk messages with the relevant aRMMs. These risk messages are:

- CAB-LA should be used as part of a comprehensive prevention strategy;
- There is potential risk of HIV-1 drug resistance development in individuals with undiagnosed HIV-1 infection
- Strict adherence to the recommended dosing schedule is important to reduce risk of HIV-1 infection and the potential development of resistance and;
- Regular monitoring and testing are needed to confirm HIV-1 status prior to starting and during CAB-LA use

Definitions of outcome variables as follows:

- **Access** will be defined as the HCP or user having accessed and used the aRMM, to be assessed as the percentage of respondents who accessed and used the relevant aRMM.
- **Knowledge** will be defined as awareness and understanding of key CAB-LA risk messages within the relevant aRMMs for HCPs and users, to be assessed as a score based on the proportion of correct responses to knowledge-related questions specific to each risk message.
- **Attitude (HCP prescribers only)** will be defined as the perceived importance of carefully selecting individuals who will adhere to the CAB-LA regimen, in deciding to whom CAB-LA will be recommended. This will be assessed as the percentage of HCPs whose responses indicate agreement on the importance of this.
- **Behaviours** will be defined as performing the recommended actions outlined in the HCP and user aRMMs, as they relate to key CAB-LA risk messages. This will be assessed as a score based on the proportion of optimal behaviour responses to behaviour-related questions. This section will not assess use of the specific aRMMs, rather the behaviours related to the risk messages as described in the aRMMs.

Further details on outcomes assessment and analysis are provided below.

### HCP Survey

From the HCP survey, data will be collected on:

Table 5. Outcome assessment areas in HCP survey

Domain	Subdomain	Survey Topic
Experience with prescriber aRMMs	Prescribers' Guide / Checklist / Reminder Card*	
 
• Prior access to aRMM
 

Knowledge	Comprehensive HIV-1 infection prevention strategy	
 
• Knowledge of additional prevention strategies
 

	Risk of developing drug resistance	
 
• Knowledge of risk of developing resistance to CAB-LA if user acquires HIV-1 before or while taking CAB-LA or following discontinuation of CAB-LA
 
• Steps to take with suspected or confirmed HIV-1 infection in CAB-LA user
 
• Knowledge of the presence of residual concentrations of CAB-LA following discontinuation
 
• Steps when user discontinues CAB-LA; considering alternative forms of PrEP for those at risk of HIV-1 infection
 

	Importance of CAB-LA adherence	
 
• Knowledge of the importance of careful selection of individuals who agree to the CAB-LA dosing schedule
 
• Knowledge of appropriate use of oral cabotegravir including for bridging
 
• Steps when user misses oral cabotegravir dose or an injection appointment
 

	Regular monitoring/HIV-1 seroconversion	
 
• Knowledge of testing requirements for HIV-1 infection prior to initiating CAB-LA, and with each subsequent injection of CAB-LA
 

Attitudes	Importance of CAB-LA adherence (prescribers only)	
 
• HCP prescribers' perspective on the ideal adherence patterns for individuals being considered to receive CAB-LA
 

#{vault:document\_date\_\_v}

Protocol for Non-Interventional Studies PASS Studies and Non-PASS Studies (4.0) March 2024

Template Doc ID: TMF-15706807

Parent Doc ID: VQD-SOP-066694

Domain	Subdomain	Survey Topic
Behaviours	Comprehensive HIV-1 infection prevention strategy (prescribers only)	
 
• Frequency of counseling on additional prevention strategies
 
• Frequency of counseling on use of the User Guide and Patient Medication Information to gain more information
 

	Risk of developing drug resistance	
 
• HIV-1 status confirmation prior to prescribing CAB-LA and throughout use (prescribers only)
 
• Frequency of counseling on steps if individual has suspected or confirmed HIV (prescribers only)
 
• Frequency of counseling on alternative forms of PrEP among individuals considering discontinuation of CAB-LA (prescribers only)
 
• Frequency of commencing antiretroviral therapy or referring for HIV treatment among individuals with suspected or confirmed HIV-1 diagnoses
 

	Importance of CAB-LA adherence (prescribers only)	
 
• Frequency of carefully selecting individuals who will adhere to the CAB-LA dosing schedule prior to prescribing
 
• Frequency of counseling on importance of adherence to dosing schedule
 
• Frequency of counseling on booking next appointments
 

	Regular monitoring/HIV-1 seroconversion	
 
• Frequency of risk assessment and HIV-1 testing (prescribers only)
 
• Frequency of counseling on importance of regular HIV screening (prescribers only)
 
• Steps taken when user misses a scheduled injection visit (not part of KAB scoring)
 

	Management of those with suspected or confirmed HIV	
 
• Steps taken for suspected/confirmed HIV
 

\* The question in the HCP survey about the Reminder Card specifically asks if the HCP or any member of their care team has ever accessed the Apretude Injection Appointment Reminder Card, which they provide to Apretude users (this question is not scored, it is

only included to better understand HCPs’ general experience of accessing Apertude aRMMs).

The full list of variables for the HCP primary objective survey are available in Annex 2.

User survey

From the user survey, data will be collected on:

